
- To determine the safety and toxicity profile and the maximum tolerated dose (MTD) of the four-drug combination of CC-486 (5-azacitidine), romidepsin, lenalidomide and dexamethasone in patients with TCM

Eligibility:

- Refractory/relapsed TCM (excluding in Cutaneous T-Cell Lymphoma) defined as follows:
 - Patients with systemic disease
 - Have received at least one line of prior therapy
 - Must have received brentuximab vedotin if the disease is anaplastic large cell lymphoma or CD30-positive cutaneous T-cell lymphoma
- Age \geq 18 years of age
- ECOG performance status of \leq 2 (or \leq 3 if decrease is due to the disease)
- Histologically or cytologically confirmed relapsed and/or refractory mature TCM
- Adequate organ and marrow function

Design:

- Open-label, single-center, uncontrolled Phase 1 study

- “3 + 3” design will be used to determine the MTD of dose-escalated lenalidomide with fixed dose of romidepsin and CC-486 (5-azacitidine)
- An expansion cohort of 9 patients will be evaluated at the MTD
- Maximum 6 cycles (28-day cycle) of combination therapy
- To explore all dose levels, including further evaluation in a dose expansion cohort, the accrual ceiling will be set at 30 patients

STATEMENT OF COMPLIANCE

The trial will be carried out in accordance with International Council for Harmonisation Good Clinical Practice (ICH GCP) and the following:

- United States (US) Code of Federal Regulations (CFR) applicable to clinical studies (45 CFR Part 46, 21 CFR Part 50, 21 CFR Part 56, 21 CFR Part 312, and/or 21 CFR Part 812)

National Institutes of Health (NIH)-funded investigators and clinical trial site staff who are responsible for the conduct, management, or oversight of NIH-funded clinical trials have completed Human Subjects Protection and ICH GCP Training.

The protocol, informed consent form(s), recruitment materials, and all participant materials will be submitted to the Institutional Review Board (IRB) for review and approval. Approval of both the protocol and the consent form must be obtained before any participant is enrolled. Any amendment to the protocol will require review and approval by the IRB before the changes are implemented to the study. In addition, all changes to the consent form will be IRB-approved; an IRB determination will be made regarding whether a new consent needs to be obtained from participants who provided consent, using a previously approved consent form.

TABLE OF CONTENTS

PRÉCIS	2
STATEMENT OF COMPLIANCE	4

1 INTRODUCTION

1.1 STUDY OBJECTIVES

1.1.1 Primary Objective

- Determine the safety and toxicity profile and the maximum tolerated dose (MTD) of lenalidomide given as part of a four-drug combination treatment with romidepsin, CC-486 (5-azacitidine) and dexamethasone to patients with mature T-cell malignancies (TCM).

1.1.2 Secondary Objectives

- Evaluate the potential antitumor activity of the romidepsin, CC-486 (5-azacitidine) and lenalidomide combination by assessing the overall response rate (ORR), complete response (CR) rate, duration of response (DOR), progression-free survival (PFS), event-free survival (EFS), and overall survival (OS).

1.1.3 Exploratory Objectives

- Evaluate changes in peripheral blood immune cell subsets and cytokine profiles, and correlation of these changes with clinical outcome.
- Evaluate changes in circulating tumor DNA to identify potential prognostic or predictive markers in patients with T-cell malignancies.
- Collect and store peripheral blood and other tissue samples for future correlative studies.

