2.5.2 Arms

Number	Name	Description
1	Experimental Treatment: Dose Escalation (Closed: prior amendment 12/07/2022)	Lenalidomide by oral intake at escalating doses of 5, 10, 15, or 20 mg/day on days -7 to 10 of each 21-day cycle (max 6 cycles) with CC-486 (5-azacitidine) at 300mg/day by oral intake on days 1-10, romidepsin at 12mg/m ² by IV infusion on Day 1 and 10 and dexamethasone at 40mg by oral intake on days 1 and 10 of each cycle, to determine MTD
2	Experimental Treatment: Dose Expansion(Closed: with amendment 12/07/2022)	Lenalidomide by oral intake at 20mg on days 1 to 10 of each 28-day cycle (max 6 cycles) with CC-486 (5-azacitidine) at 300mg/day by oral intake on days 1-10, romidepsin at 12mg/m ² by IV infusion on Day 1 and 10 and dexamethasone at 40mg by oral intake on days 1 and 10 of each cycle
3	Experimental Treatment: Dose Expansion	Lenalidomide by oral intake at 20mg (MTD) on days 1 to 10 of each 28-day cycle (max 6 cycles) with CC-486 (5-azacitidine) at 300mg/day by oral intake on days 1-10, romidepsin at 12mg/m ² by IV infusion on Day 1 and 10 and dexamethasone at 40mg by oral intake on days 1 and 10 of each cycle

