3 STUDY IMPLEMENTATION

3.1 STUDY DESIGN

To determine the maximum tolerated dose (MTD), and the safety and toxicity profile of the combination of lenalidomide, CC-486 (5-azacitidine) and romidepsin in patients with refractory/relapsed TCM, a phase 1 open-label, non-randomized, single-center study will be conducted at the NCI. A standard “3 + 3” design will be used to determine the MTD of dose-escalated lenalidomide in combination with fixed doses of CC-486 (5-azacitidine), romidepsin (R) and dexamethasone (D) with an expansion cohort at the MTD.

In patients with relapsed or refractory TCM, lenalidomide will be administered by oral intake in a dose-escalation with a starting dose of 5mg daily, a second dose level of 10mg daily, a third dose level at 15mg daily, and a fourth dose level at 20mg daily on days -7 to day 10 of first cycle (see **Table 1** for additional dose levels and schedules, cycles are 21 days each). After the second cycle, lenalidomide will be given from day 1 to day 10 in each cycle for up to six cycles. CC-486 (5-azacitidine) with a dose of 300mg oral intake daily will be given on day 1 to day 10, romidepsin will be administered at a dose of 12 mg/ m² on days 1 and 10 (±2 days) and dexamethasone will be given on day 1 and 10 (±2 days) of the cycle.

After approval of Amendment 12/07/2022: Participants will receive six cycles (each 28 days in length) of: lenalidomide at the MTD from day 1 to day 10, CC-486 (5-azacitidine) at a dose of 300mg oral intake daily given on day 1 to day 10, romidepsin administered at a dose of 12 mg/ m² on days 1 and 10 (±2 days) and dexamethasone on day 1 and 10 (±2 days) of the cycle.

Treatment will continue for a maximum of 6 cycles or until toxicity (i.e., dose limiting toxicity) as found in Section 3.9 or toxicity requiring discontinuation as defined in Section 3.5) or progressive disease.

The treatment will be repeated for up to 6 cycles. The patients are allowed to proceed to stem cell transplantation (SCT) if eligible during and after the protocol treatment. Patients who undergo SCT before all 6 cycles of protocol treatment are administered will be taken off therapy. All patients who undergo SCT will continue to be followed for survival, but not for toxicity (see Section 3.8)

Cycles 1-6												28
Azacitidine												by mouth once per day
Lenalidomide												by mouth once per day
D												D
R												R

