5 CORRELATIVE STUDIES FOR RESEARCH

5.1 BIOSPECIMEN COLLECTION

5.1.1 Summary

This study will test the feasibility of concomitant NFκ-B inhibition with lenalidomide and epigenetic modification with CC-486 (5-azacitidine) and romidepsin in patients with T-cell malignancies. Although increased efficacy with the combination has been demonstrated *in vitro*, effects of the combined treatment on the tumor microenvironment, circulating immune cell subsets, cytokine production, and exosome composition are not known. The correlative studies performed in this trial will focus on how lenalidomide alone and in combination affects tumor cells, immune cell subsets, and cytokines in tumor tissue and peripheral blood, and whether these may represent a predictive or prognostic biomarker in patients with TCMs.

Composition of the tumor microenvironment will be analyzed via immunohistochemistry, flow cytometry, and single-cell RNAseq before treatment, after 7 days of single-agent lenalidomide, and after 15 days of combined treatment with lenalidomide, romidepsin, and CC-486 (5-azacitidine). Differences in circulating immune cell subsets associated with administration will be followed throughout treatment to both study the effects of combined therapy on the immune system, and to identify potential biomarkers that would be predictive of response. Circulating tumor DNA and exosome composition will be followed and analyzed with the same goal in mind. Germline DNA will be sequenced to distinguish circulating tumor DNA from other cell-free DNA.

Sample	Collection Details*	Time Points [†]							Supervising Laboratory/ Investigator [^]
		Baseline ⁴ (C1 D-7)	C1 D1	C1 D10	C1 D15	C2-6 D1	C2-6 D10	Follow-up [#]	
Blood Samples									
Lymphocyte subset testing	• 2 x 10mL K ₂ EDTA (lavender-top) tubes	X	X	X	(X)		(X)	(X) ¹	DLM
PBMC banking	• 3 x 10mL Na-heparin (green-top) tube	X	X	X	(X)	X	(X)	X	Leidos CSL
Circulating tumor DNA, plasma banking**	• 1 x 10mL K ₂ EDTA tube • 1 x 10mL Streck/BCT tube	X	X			X		X ²	Leidos CSL
Tissue Samples									
Tissue immune cell subsets	• Two core biopsy samples in RPMI 1640 with 10% human serum and antibiotics • One core biopsy sample in formalin NOTE: Samples may be tumor tissue or bone marrow aspirate/biopsy	X***	(X)		(X)			(X) At disease progression	(RPMI 1640 and DLM/ NCI LP (formalin))

Sample	Collection Details*	Time Points [†]							Supervising Laboratory/ Investigator [^]

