		Baseline ⁴ (C1 D-7)	C1 D1	C1 D10	C1 D15	C2-6 D1	C2-6 D10	Follow-up [#]	
Other Samples									
Germline DNA	• Blood, Buccal Swab, or Saliva (preferred) – see 5.4	X							Leidos CSL
(X) = Optional; samples will be collected if adequate time/staff available for processing, and if research blood drawn is less than the allowed limit noted in Section 5.1.3 . If an optional sample is not collected at baseline, it would also not be collected in follow-up unless specifically requested by the PI.									
[†] The location of specimen processing or analysis may be adjusted with the permission of the PI or laboratory investigator.									
*Tubes/media may be adjusted at the time of collection based upon materials available or to ensure the best samples are collected for planned analyses.									
** May be omitted if research blood drawn would be over the allowed limit noted in Section 5.1.3 .									
*** Tumor biopsy (bone marrow, skin, or ultrasound-guided LN biopsies) is required if archival tissue is not available or adequate; otherwise, this is optional									
[†] All time points during treatment are ± 3 days. All follow-up time points are ± 7 days.									
#Subjects who discontinue treatment for a reason other than disease progression and who do not start new treatment should continue to have study bloods collected at the scheduled time points.									
¹ At the end of treatment only.									
² At each follow-up visit prior to disease progression, as specified in Section 3.8.2 .									
⁴ With the exception of tissue immune cell subset (if applicable) and Germline DNA which are to be collected during Baseline, samples correlating to the lead-in window will no longer be collected as the lead-in window has been retired.									

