5.5.2 Immune Subset Analysis

Peripheral blood mononuclear cells (PBMC) will be assessed using multiparameter flow cytometry for immune subsets including but not necessarily limited to CD8+ T-cells, CD4+Foxp3- T-cells, Tregs, T_{ex}, Th1, Th2 and Th17+ CD4+ T-cells, NK cells and subsets, monocyte subsets, MDSC

subsets. Assessment may include functional markers, i.e. PD-1, Tim-3, CTLA-4, PD-L1, HLA-DR, Ki67 and/or CD40.

5.5.3 cfDNA/ctDNA

Since the methods of molecular monitoring in the peripheral blood is an emerging field with numerous technologies under development, the storage of peripheral blood mononuclear cells (PBMC), serum, and plasma will all be performed allowing for future comparison of the different compartments for analytes that include cell-free circulating tumor DNA (ctDNA), and RNA sequencing of circulating tumor cells. Studies to be performed on these samples include: cfDNA/ctDNA for liquid genotyping as a non-invasive dynamic monitoring of disease as well as monitoring for individual molecular aberrations that herald progression or disease transformation; specifically, amplification and sequencing of the VDJ segment of the immunoglobulin receptor is planned. Germline DNA obtained from saliva, blood, or buccal mucosa will be used to discriminate somatic from germline mutations during cfDNA and ctDNA analyses.

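### In Arm 3 no plasma draw is scheduled while patients are on drug, so an on-drug cytokine change can be studied only from optional or unspecified material

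*Combined protocol and SAP*

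**What the plan says.** The exploratory objective in Section 1.1.3 is to "Evaluate changes in peripheral blood immune cell subsets and cytokine profiles, and correlation of these changes with clinical outcome". Section 5.1.1 describes the focus of the correlative studies as "how lenalidomide alone and in combination affects tumor cells, immune cell subsets, and cytokines in tumor tissue and peripheral blood".

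In the 5.1.1 sample table the only row that yields plasma is "Circulating tumor DNA, plasma banking". It is marked at Baseline (C1 D-7), C1 D1, C2-6 D1 and Follow-up. The cells for C1 D10, C1 D15 and C2-6 D10 are empty. For follow-up, note 2 reads "At each follow-up visit prior to disease progression, as specified in Section" 3.8.2. Note 4 says that "samples correlating to the lead-in window will no longer be collected as the lead-in window has been retired", with exceptions only for tissue immune cell subsets and germline DNA.

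The current regimen, Arm 3 in Section 2.5.2, is "Lenalidomide by oral intake at 20mg (MTD) on days 1 to 10 of each 28-day cycle (max 6 cycles". CC-486 is given on the same days. Section 3.1 has "romidepsin administered at a dose of 12 mg/ m² on days 1 and 10 (±2 days", and dexamethasone on the same two days.

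Section 5.5.3 states that "the storage of peripheral blood mononuclear cells (PBMC), serum, and plasma will all be performed", but it gives no time points, and the table has no serum tube. No method in Sections 5.5.1 to 5.5.4 is a cytokine assay.

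**The concern.** A question about how drugs affect cytokines is best answered by comparing a sample taken before dosing with one taken during it. Under the lead-in design the table supplied such a pair for lenalidomide alone: day −7 before the first dose, and C1 D1 after up to 7 days of it. Once the lead-in was retired, C1 D1 became the start-of-treatment sample, and no draw was moved into the dosing period to take over its role.

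The two halves of the objective are now treated unequally. Tubes for lymphocyte subsets and for PBMC are required at C1 D10, a dosing day; plasma is not. Plasma is also the one row that its footnote allows to be dropped if the research blood limit would be exceeded.

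At stake is whether Arm 3, the only arm still enrolling and the one that gives all four drugs from day 1, will yield any planned observation of cytokines under treatment.

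**Working it through.** The plan states no figure for the gap between dosing and sampling, so there is none to reproduce. The check reads the sample table against the dosing calendar.

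**Inputs**
- Plasma time points: 5.1.1 table.
- Sampling window during treatment: ±3 days (5.1.1 footnote).
- Oral drugs: days 1 to 10 of a 28-day cycle (2.5.2, Arm 3).
- Romidepsin and dexamethasone: days 1 and 10, ±2 days (3.1).
- Earlier design: 21-day cycle with a 7-day lenalidomide lead-in (3.4.1).

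**Gap from last dose to the next D1 plasma** = (cycle length + 1) − last dosing day
- 28-day cycle: 29 − 10 = 19 days.
- With the sample moved ±3 days: 19 − 3 = 16 to 19 + 3 = 22 days.
- If the day-10 infusion also moves ±2 days: 26 − 12 = 14 to 32 − 8 = 24 days.
- Earlier 21-day cycle: 22 − 10 = 12 days (9 to 15 with ±3).

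The upper part of each range needs care. If the new cycle starts on day 29, a D1 draw taken late in its window comes after that cycle's first dose. The sample table does not require a pre-dose draw.

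**Plasma draws in Arm 3 while on drug**
- C1 D1: nominally the start of treatment, so not on drug.
- C2 to C6 D1: 5 draws, each nominally 19 days after the last dose.
- Follow-up: after treatment has ended, so off drug.
- Planned draws between the first dose and day 10 of any cycle: 0, out of 1 + 5 = 6 scheduled D1 draws. Section 2.6.4 still lists blood for ctDNA at baseline; even if that draw is made, it is before treatment.

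**On-drug blood that is collected or could be used**
- C1 D10, required: 2 × 10 mL EDTA for lymphocyte subsets and 3 × 10 mL Na-heparin for PBMC, 20 + 30 = 50 mL.
- C1 D10 and C2-6 D10: routine CBC (3.9). Section 5.1.3 permits leftover plasma from such tubes to be used for research but does not schedule it.

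**Comparison lost with the lead-in**
- Before: day −7 against C1 D1, lenalidomide alone.
- Now: none. The planned schedule did not provide on-drug plasma for the combination under the earlier design either.

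**The case against.** Several points on the other side are sound.

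- A reader might infer that cytokine change cannot be measured at all. The documents do not support that. The objective speaks of changes without saying they must be on drug, and change from C1 D1 to later D1 and follow-up samples can be measured and related to outcome. Section 5.1.3 allows retrieval of leftover plasma, and the required C1 D10 PBMC could support cell-based readouts. Neither route is planned or specified for cytokines, so the gap in planned sampling stands.
- A reader might infer that plasma is taken only on day 1 of cycles. It is also banked at follow-up visits before progression, although off drug.
- A reader might link the gap to the cytokine-release toxicity that led to removal of the lead-in. That link is weak: Section 1.10.3 ties the signal to CTCL participants on single-agent lenalidomide, while the expansion cohort excludes CTCL (2.1.2.4, 2.5.1) and Arm 3 gives no single-agent period.
- The absence of a named assay is largely answered by Section 5.5, which defers methods until samples are ready and foresees an amendment if needed.
- The scale is small. Section 3.4.1 reports 20 patients enrolled before the change, and the lead-in comparison was scheduled for patients under that design, although the lead-in could be shortened. The analysis is exploratory (10.4.8).
- No pooling of D1 values across the two designs is planned, so confusion between them is a risk to guard against, not an error in the plan.
- A C1 D10 draw is not on drug automatically. With ±3 days it may fall on day 7 to day 13, and days 11 to 13 are past the last scheduled oral dose. Any remedy must deal with this.

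**Conclusion.** The point holds as a gap in planned sampling for Arm 3, of minor weight. As scheduled, none of the six D1 plasma draws is on drug, and the later five fall about 19 days after the last dose (16 to 22 with the sampling window). The stated interest in how the drugs affect blood cytokines therefore rests, in this arm, on optional leftover plasma or on PBMC assays that the plan does not describe.

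It concerns up to 6 additional evaluable patients, the Cohort 2 ceiling in Section 2.5.1. The objective remains partly answerable, so there is no case for deleting it.

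The figures assume that cycles start on time and that D1 samples are drawn before that day's dose. A delayed cycle would lengthen the gap. A D1 draw made after dosing would be on drug by accident and not by design.

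**What to change.** 1. In the 5.1.1 table, mark a plasma aliquot at C1 D1 and C1 D10, taken from the Na-heparin PBMC tubes already required on both days. This gives a pair matched on tube type, and these tubes already go to the laboratory that receives the banked plasma.
2. Require the C1 D1 draw to be pre-dose.
3. Place the C1 D10 draw within the dosing period, and record its time relative to the last oral dose and to that day's romidepsin and dexamethasone.
4. In 10.4.8, define the on-drug cytokine change as C1 D10 minus C1 D1. State that C1 D1 values from lead-in patients, taken on lenalidomide, are not pooled with C1 D1 values from Arm 3, taken before treatment.

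The cost is a table entry, a few sentences, and a small amount of aliquoting, labelling and storage. There are no extra visits and no extra blood: the C1 D10 research draw stays at 50 mL.

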1.2 BACKGROUND

1.2.1 Peripheral T-cell lymphoma

Peripheral T-cell lymphoma (PTCL) is a rare heterogeneous group of neoplasms in mature T-cell malignancies (TCM) which account for 5-10% of all lymphomas. Currently, the World Health Organization (WHO) classification combines mature T- and NK-cell neoplasms under the umbrella term PTCL and the category is composed of 24 different entities, based on the different morphologic, phenotypic, molecular, and clinical features, including disease site [1]. Compared with B-cell lymphomas, many types of PTCL develop not in lymph nodes, but in specific extranodal sites such as extranodal NK/T cell lymphoma, nasal type (ENKL) in the nasal cavity, enteropathy-associated T-cell lymphoma (EATL) in the small intestine and hepatosplenic T-cell lymphoma (HSTL) in the liver and spleen. The most common histologic subtype is peripheral T-cell lymphoma, not otherwise specified (PTCL-NOS), followed by angioimmunoblastic T-cell lymphoma (AITL) or anaplastic large cell lymphoma (ALCL), either ALK positive (ALK+) or ALK negative (ALK-) and these three types account for about 60% of all cases of PTCLs [2], however, it is still rare that the age-adjusted incidence in the U.S. for PTCL-NOS, AITL and ALCL is 0.30, 0.05 and 0.25 per 100,000 person-years, respectively [3-5].

The presentation of patients with PTCL largely depends on the subtype. PTCL-NOS, AITL, and ALCL often present with generalized lymphadenopathy, and there is also frequent involvement of the skin, gastrointestinal tract, liver, spleen, and bone marrow. In contrast, a number of rare specific subtypes, such as ENKL, HSTL, and EATL, present with primarily with extranodal disease, and other subtypes, such as adult T-cell leukemia (ATL) and T prolymphocytic leukemia (T-PLL), may have a leukemic presentation. Advanced stage disease (stages III and IV) is common for most of these diseases, constituting 69% of PTCL-NOS 69%, 89% of AITL, 65% of ALK+ALCL, 58% of ALK-ALCL, 69% of EATL, and 90% of HSTL.

1.2.2 Cutaneous T-cell lymphoma

Cutaneous T-Cell Lymphomas (CTCLs) are a clinically heterogeneous subgroup of PTCL/TCM, accounting for most lymphomas arising in skin. Mycosis fungoides (MF) and Sézary syndrome (SS) are defined by their cutaneous lesions that result from the accumulation of a T-helper memory/effector subset with a CD4+, CD8-, CD45RO+CLA+ phenotype in skin and blood [1]. Most commonly, MF starts as an indolent and chronic dermatitis in the sun shielded areas. The incidence of CTCL was initially increased and now it is plateaued with currently 1.0 per 100,000 person/year, based on Surveillance, Epidemiology, and End Results (SEER) registry data, with the highest incidence rates being reported among males and African-Americans [6].

1.2.3 Treatment of relapsed/refractory PTCL and CTCL

Excluding a small proportion of indolent subtypes, PTCL is often treatment-resistant and is associated with poor prognosis [7]. Patients with systemic TCM are most commonly treated with CHOP (cyclophosphamide, doxorubicin, vincristine and prednisone)-like therapy, which is associated with long-term progression-free survival of about 30% [8-10]. Previous reports showed that the median PFS and OS after the first recurrence or disease progression were generally less than one year particularly without stem cell transplant [11-13]. British Columbia Cancer Agency reported that there was only a small difference in the OS between patients who received chemotherapy and those who did not (6.5 vs 3.7 months, respectively), indicating the need for new treatment strategies [13].

Early stage MF is characterized by eczematous or psoriasiform dermatitis covering < 80% body surface area without evidence of blood or visceral involvement. As the majority of CTCL patients present with patch/plaque stage MF and have an excellent prognosis, the initial goal of therapy is to improve symptoms and quality of life while avoiding treatment-related toxicity. Early MF is usually indolent and treated with combination skin-directed therapy. However, once they stopped responding to topical treatment or transformed to SS when needing systemic treatment, the prognosis remains poor with median PFS of less than a year [14].

[figure not shown]
Over the last decade, the U.S. Food and Drug Administration (FDA) approved several drugs with novel mechanisms of action for the treatment of patients with recurrent PTCL including cutaneous T-cell lymphoma (CTCL); these included vorinostat in 2006, pralatrexate in 2009, brentuximab vedotin (BV) for ALCL in 2011, romidepsin in 2011, belinostat in 2014 and mogamulizumab in 2018.

While these drugs are additions to the therapeutic options, they are approved by the response rate not by survival benefit, although response rates were generally less than 30% with the exception of BV for patients with ALCL, and an actual impact on long-term outcome is not proven. MD Anderson Cancer Center retrospectively analyzed 321 patients with PTCL-NOS and AITL and found that the median PFS after pralatrexate and romidepsin as single agents were 3.0 and 2.5 months, respectively which was not significantly different from chemotherapy approach [11]. Also, meta-analysis of available treatments for relapsed/refractory PTCL showed that even though approved, belinostat and pralatrexate have lower safety than several other regimens (**Figure 1**) [15].

These studies indicate that even with the recent new drug approvals, single agent efficacy is limited for all these drugs, that there has been no significant improvement in survival even with multiple successive salvage treatments, and that new therapies with higher efficacy and improved safety

profile are needed.

Figure 1: Safety and efficacy of treatments for relapsed/refractory PTCL

